Section 2.3.1 Risk Assessment	Updated rationale for risk of progression of heart failure	To provide information based on current data	Non-substantial

Section # and Name	Description of Change	Brief Rationale	Substantial/ Non-substantial
Section 4.1 Overall Design; Section 9.2 Sample Size Determination	Change to permit not capping randomisation of participants not included in exploratory cough sub-study solely to achieve target sample size of the sub-study	To avoid completion of exploratory sub-study delaying completion of study overall	Non-substantial
Section 5.1 Inclusion Criteria	Criterion 11: Increased the maximum permitted BMI to 40 kg/m ²	To maintain consistency with other MEDI3506 studies in context of other exclusion criteria	Substantial
Section 5.1 Inclusion Criteria	Criterion 19: Changed historic exacerbation requirement from one in 12 months to one in 24 months	To adapt to sustained fall in real world exacerbation rates secondary to the ongoing COVID-19 pandemic	Substantial
Section 5.2 Exclusion Criteria	Criterion 1: Removed the exclusion of all participants who test positive for SARS-CoV-2 at SV1. All participants who test positive at SV2 continue to be excluded.	To permit participants who test positive for SARS-CoV-2 at SV1, but negative at SV2 and who do not have symptoms meeting any other exclusion criterion to be randomised.	Substantial
Section 5.2 Exclusion Criteria	Criterion 3: Rewritten	Revised text to be clearer and consistent with other AstraZeneca studies	Substantial
Section 5.2 Exclusion Criteria; Section 1.3 Schedule of Activities, Table 1 Footnote i	Criterion 5: Removal of entire criterion which excluded participants with an NT-proBNP above the upper limit of normal.	Not considered to provide additional benefit to participant safety given other mitigations, including screening echocardiograms	Substantial

Section # and Name	Description of Change	Brief Rationale	Substantial/ Non-substantial
Section 5.2 Exclusion Criteria	Criterion 13: Removed the reference to HbA1c	To permit investigator judgement as to whether Type 2 diabetes is well controlled (and hence not exclusionary) and to maintain consistency with other MEDI3506 studies	Substantial
Section 6.5.5 COVID-19 Vaccination	Removed dose from list of information to be recorded	Information is generally not available	Non-substantial

1 PROTOCOL SUMMARY

1.1 Synopsis

Protocol Title: A Phase II, Randomised, Double-blind, Placebo-controlled Study to Assess the Efficacy and Safety of MEDI3506 in Adult Participants with Uncontrolled Moderate-to-severe Asthma

Short Title: Study to Assess the Efficacy and Safety of Subcutaneously Injected MEDI3506 in Adults with Uncontrolled Moderate-to-severe Asthma

Rationale:

The MEDI3506 pre-clinical profile suggests that MEDI3506 can reduce asthmatic airway inflammation, improve epithelial integrity, reduce mucus production, and improve muco-ciliary transport. As such, MEDI3506 is hypothesised to impact asthma disease status by increasing forced expiratory volume in the first second (FEV₁, and other physiological measures of lung function) and reducing frequency and severity of asthma exacerbations, thereby improving quality of life. This Phase II study aims to assess the efficacy and safety of MEDI3506 in adult participants with uncontrolled moderate-to-severe asthma.

Objectives and Endpoints

Objective	Endpoint
Primary	
To assess the effect of MEDI3506 compared with placebo on lung function, in adult participants with uncontrolled moderate-to-severe asthma.	As measured in clinic, change from baseline to Week 16 in pre-BD FEV ₁ (L).
Secondary	
To further assess the effect of MEDI3506 compared with placebo on lung function, in adult participants with uncontrolled moderate-to-severe asthma.	As measured in clinic, change from baseline to Weeks 8 and 16 in post-BD FEV ₁ (L).
To assess the PK of MEDI3506 in adult participants with uncontrolled moderate-to-severe asthma.	Serum MEDI3506 concentration-time profiles during the intervention and follow-up periods.
To assess the immunogenicity of MEDI3506 in adult participants with uncontrolled moderate-to-severe asthma.	ADA during the intervention and follow-up periods.
To assess the effect of MEDI3506 compared with placebo on asthma control in adult participants with uncontrolled moderate-to-severe asthma.	Change from baseline to Week 16 in ACQ-6 score. Proportion of participants with a decrease in ACQ-6 score of ≥ 0.5 from baseline to Week 16. Proportion of participants achieving ACQ-6 well controlled status (defined as ACQ-6 score ≤ 0.75 at Week 16).

Objective	Endpoint
To assess the effect of MEDI3506 compared with placebo on health status in adult participants with uncontrolled moderate-to-severe asthma.	Change from baseline to Week 16 in SGRQ score. Proportion of participants with a decrease in SGRQ total score of ≥ 4 points from baseline to Week 16.
To assess the effect of MEDI3506 compared with placebo on CompEx in adult participants with uncontrolled moderate-to-severe asthma.	Time to first CompEx event based on the period from baseline to Week 16. CompEx annualised event rate.
To assess the effect of MEDI3506 compared with placebo on concentration of FeNO in adult participants with uncontrolled moderate-to-severe asthma.	Percent change from baseline to Week 16 in concentration of FeNO in exhaled breath.

ACQ-6 = asthma control questionnaire-6; ADA = anti-drug antibody(ies); BD = bronchodilator; CompEx = composite endpoint for severe exacerbations of asthma; FeNO = fractional exhaled nitric oxide; FEV₁ = forced expiratory volume in the first second; L = litre(s); PK = pharmacokinetics; SGRQ = St George’s respiratory questionnaire.

For safety and exploratory objectives and endpoints, see Section 3 of the protocol.

Overall Design

Study D9181C00001 is a Phase II, randomised, double-blind, placebo-controlled, parallel-group, proof-of-concept study to evaluate the efficacy, safety, pharmacokinetics (PK) and immunogenicity of MEDI3506 in adult participants with uncontrolled moderate-to-severe asthma on standard of care (SOC). The study has 3 treatment-arms. Participants who fail screening can be re-screened.

Disclosure Statement: This is a parallel group treatment study that is participant-, investigator-, and sponsor-blinded.

Number of Participants:

Approximately 228 participants will be randomised to achieve 216 evaluable participants.

Intervention Groups and Duration:

Participants will be randomised in a 1:1:1 ratio to receive **CC1** mg MEDI3506, **CC1** mg MEDI3506, or placebo every **CC1** by subcutaneous (SC) injection for a total of **CC1** doses.

Participants will be enrolled in this study for up to 29 weeks. The study comprises of 3 periods including the screening period of up to 5 weeks, an intervention period of 16 weeks, and a follow-up period of 8 weeks.

Data Monitoring Committee:

A Data Safety Monitoring Board (DSMB) has been established to oversee the MEDI3506 clinical development programme. In addition to a full DSMB 6-month periodic review of safety data, the DSMB chair will review unblinded safety data summaries every 3 months; the DSMB can meet on an ad hoc basis.

Statistical Methods

A sample size of 216 participants (72 participants per treatment group), randomised 1:1:1 to MEDI3506 **CCI** mg: MEDI3506 **CCI** mg: placebo, will provide at least 80% power to detect a statistically significant difference in change from baseline to Week 16 in pre-bronchodilator (BD) FEV₁, assuming a difference of 150 mL between placebo and MEDI3506, a between-participant standard deviation (SD) of 420 mL and a one-sided-10% alpha level. To allow for 5% participants being ineligible for the primary analysis, a total of approximately 228 participants will be randomised (approximately 76/arm).

Efficacy analyses will be performed using the ITT population. The primary estimand is a ‘Treatment Policy’ estimand, as follows: the difference in mean change from baseline in FEV₁ at Week 16 (MEDI3506 – placebo) will be estimated using a repeated measures mixed effects analysis of covariance model, for the ITT population. This will include all available data from all visits up to and including Week 16, irrespective of whether the participant discontinued study intervention or received rescue therapy.

A similar approach will be taken for the analysis of asthma control questionnaire-6 (ACQ-6), St George’s respiratory questionnaire (SGRQ), and fractional exhaled nitric oxide (FeNO). The difference in mean change from baseline in post-BD FEV₁ at Weeks 8 and 16 will be estimated using a repeated measures mixed effects analysis of covariance model, similar to that described for the primary efficacy analysis. Data may be log-transformed prior to analysis where appropriate. Time to first composite endpoint for severe exacerbations of asthma (CompEx) event will be analysed using a Cox proportional hazard model, with treatment fitted as a covariate.

MEDI3506 serum concentrations will be tabulated along with descriptive statistics. Mean and individual serum MEDI3506 concentration-time profiles will be plotted. Population PK modelling may be performed if data allow. Positive antibodies to MEDI3506 will be reported by treatment group. If there is a high incidence of anti-drug antibody (ADA), the association of ADA with MEDI3506 concentration will be assessed.

1.2 Schema

The general study design is summarised in [Figure 1](#).

CCI

CCI

1.3 Schedule of Activities

Once informed consent has been obtained, eDiary provision and training for site and home visits should occur first during SV1, followed by patient reported outcome (PRO) assessments. PRO assessments should be conducted first at all other visits. For all participants, in-clinic spirometry testing must be initiated between 6:00 AM and 11:00 AM during the screening or re-screening period, and randomisation visit (SV4). Whenever electrocardiograms (ECGs), vital signs, and blood draws are scheduled for the same nominal time, the order should be as follows: ECG, vital signs (vital signs can occur immediately after ECG using the same rest period), then blood draws. The timing of the first 2 assessments should be such that it allows the blood draw (eg, PK blood sample) to occur at the assigned nominal time. Whenever FeNO, airwave oscillometry (AO), and spirometry are scheduled for the same nominal time, the order should be as follows: FeNO, AO, then spirometry. Nasal sampling should be performed last, with nasal lining fluid collection performed before nasal epithelium collection (when both are scheduled). Urine samples may be collected at any time during the study visit (when scheduled). On days when investigational product is administered, all assessments should be performed pre-dose unless otherwise specified in the Schedule of Activities. Refer to Section 8 for additional information on assessment ordering (eg, pre-, post-dose or multiple timepoints within a visit). In the event that a clinical laboratory test result is not available from central laboratories during the screening period, see Section 8.2.7.

Table 1 Schedule of Activities: Screening Period

Visit Number	SV1	SV2	SV3
Procedure/Study Day	-35 to -28	-14 to -6	Visit no longer needed
Study Week	-4	-1	
Written ICF CCI /assignment of SID number	X ^a		
Written informed consent for future use and/or DNA analysis (optional)	X		
Verify eligibility criteria	X	X	
Demographics	X		
Baseline asthma assessments			
Provision of, and training on use of, home spirometry device and eDiary	X		
ACQ-6	X	X	
SGRQ		X	
SNOT-22 (comorbid CRS participants only)	X		
At-home eDiary completion and spirometry use	Twice daily throughout screening period		

Table 1 Schedule of Activities: Screening Period

Visit Number	SV1	SV2	SV3
Procedure/Study Day	-35 to -28	-14 to -6	Visit no longer needed
Study Week	-4	-1	
Assess adherence to at-home eDiary completion, spirometry, and SOC medication use		X	
Assessment of asthma exacerbations		X	
FeNO	X	X	
Airwave oscillometry		X	
In-clinic spirometry (pre-BD)	X	X	
In-clinic spirometry (post-BD)	X ^b	X ^c	
Safety assessments			
Concomitant medications	X	X	
Medical, surgical, and asthma history	X		
Physical examination (complete)	X		
Weight and height	X		
Vital signs	X		
ECG	X		
Echocardiogram		X ^d	
SARS-CoV-2 PCR test	X ^e	X ^f	
Assessment of AEs/SAEs	X	X	
Collect blood for:			
Haematology	X		
Coagulation parameters	X		
Serum chemistry	X		
Serum pregnancy test ^g	X		
FSH (if needed to confirm post-menopausal status in female participants aged < 50 years and not on HRT)	X		
HbA1c	X		
Hepatitis B (HBsAg, anti-HBs, anti-HBc), and C; HIV-1 and HIV-2	X		
IGRA (TB test) ^h	X		
NT-proBNP	X		
Exploratory biomarkers (serum)	X		
Total IgE (serum)	X		
EDN (plasma)	X		

Table 1 Schedule of Activities: Screening Period

Visit Number	SV1	SV2	SV3
Procedure/Study Day	-35 to -28	-14 to -6	Visit no longer needed
Study Week	-4	-1	
Collect urine for:			
Urinalysis	X		
Urine pregnancy test ^g		X	
Pandemic impact assessment		X	
Exploratory cough sub-study only			
At-home cough monitoring (for the 24 hours post-clinic visit)		X	
Cough VAS		X	

- ^a ICF may be signed prior to SV1, providing all screening visits are scheduled to take place within a 28 to 35 day timeframe.
- ^b Post-BD spirometry should be performed at SV1 if documented evidence of asthma (see Section 5.1) is not already available.
- ^c Post-BD spirometry should be performed at SV2 if documented evidence of asthma (see Section 5.1) is not already available.
- ^d May be performed any time after signing of informed consent, so that results are available prior to SV4 (randomisation).
- ^e Participants are permitted to continue screening if the result from the SARS-CoV-2 PCR test performed at SV1 has not been returned by SV2.
- ^f Test may be performed at either visit or anytime on or after Day -7 such that the results are available prior to SV4 (see Exclusion Criterion 1).
- ^g Female participants of childbearing potential only.
- ^h See Exclusion Criterion 4.

ACQ-6 = asthma control questionnaire-6; AE = adverse event; anti-HBc = hepatitis B core antibody; anti-HBs = hepatitis B surface antibody; BD = bronchodilator; CRS = chronic rhinosinusitis; ECG = electrocardiogram; EDN = eosinophil derived neurotoxin; FeNO = fractional exhaled nitric oxide; FSH = follicle-stimulating hormone; HbA1c = haemoglobin A1c; HBsAg = hepatitis B surface antigen; HIV = human immunodeficiency virus; HRT = hormone replacement therapy; ICF = informed consent form; IgE = immunoglobulin E; IGRA = interferon gamma release assay; NT-proBNP = N-terminal prohormone of B-type natriuretic peptide; SAE = serious adverse event; SARS-CoV-2 = severe acute respiratory syndrome coronavirus 2; SGRQ = St George’s respiratory questionnaire; SID = subject identification; SNOT-22 = sino-nasal outcome test-22; CCI SOC = standard of care; SV = study visit; TB = tuberculosis; VAS = visual analogue scale.

Table 2 Schedule of Activities: Study Intervention and Follow-up Periods

Period	Study Intervention							Follow-up		
Visit Number	SV4 (Randomisation)	SV5 (TC)	SV6	SV7	SV8	SV9	SV10	SV11	SV12	E/D
Study Day	1	2	8 (± 3)	29 (± 3)	57 (± 3)	85 (± 3)	113 (± 3)	141 (± 3)	169 (± 3)	
Study Week	0	0	1	4	8	12	16	20	24	
Efficacy assessments										
ACQ-6	X		X	X	X	X	X		X	X
SGRQ	X			X		X	X		X	X
SNOT-22 (comorbid CRS participants only)	X		X	X	X	X	X			
At-home eDiary completion and spirometry use	Twice daily throughout the intervention period.									
Assess adherence to at-home eDiary completion, spirometry, and SOC medication use	X	X	X	X	X	X	X	X	X	
Assessment of asthma exacerbations	X	X	X	X	X	X	X	X	X	X
PGI-BR							X			
Study participant feedback questionnaire (optional)	X						X		X	X
FeNO	X		X	X	X	X	X	X	X	X
Airwave oscillometry (pre-administration of study intervention)	X		X	X	X	X	X			
Airwave oscillometry (4 hours post-administration of study intervention)	X ^a									

Table 2 Schedule of Activities: Study Intervention and Follow-up Periods

Period	Study Intervention							Follow-up		
Visit Number	SV4 (Randomisation)	SV5 (TC)	SV6	SV7	SV8	SV9	SV10	SV11	SV12	E/D
Study Day	1	2	8 (± 3)	29 (± 3)	57 (± 3)	85 (± 3)	113 (± 3)	141 (± 3)	169 (± 3)	
Study Week	0	0	1	4	8	12	16	20	24	
In-clinic spirometry (pre-BD) (pre-administration of study intervention)	X		X	X	X	X	X	X	X	X
In-clinic spirometry (4 hours post-administration of study intervention)	X ^a									
In-clinic spirometry (post-BD)	X				X		X			
Safety assessments										
Concomitant medications	X	X	X	X	X	X	X	X	X	X
Physical examination	X ^b		X ^b	X ^c	X ^c					
Weight	X						X		X	X
Vital signs	X		X	X	X	X	X	X	X	X
ECG	X ^d						X		X	X
Echocardiogram ^e						X ^f				
Assessment of AEs/SAEs	X	X	X	X	X	X	X	X	X	X
Injection site reactions	X		X	X	X	X	X			X
SARS-CoV-2 PCR test ^g	X		X	X	X	X	X	X	X	X
Collect blood^h for:										
Haematology	X		X	X	X	X	X		X	X
Coagulation parameters	X		X	X	X	X	X		X	X
Serum chemistry	X		X	X	X	X	X		X	X

Table 2 Schedule of Activities: Study Intervention and Follow-up Periods

Period	Study Intervention							Follow-up		
Visit Number	SV4 (Randomisation)	SV5 (TC)	SV6	SV7	SV8	SV9	SV10	SV11	SV12	E/D
Study Day	1	2	8 (± 3)	29 (± 3)	57 (± 3)	85 (± 3)	113 (± 3)	141 (± 3)	169 (± 3)	
Study Week	0	0	1	4	8	12	16	20	24	
NT-proBNP ^e					X	X	X		X	X
PK (serum)	X		X	X	X	X	X	X	X	X
Immunogenicity (serum)	X		X	X	X	X	X		X	X
Exploratory biomarkers (serum)	X		X	X	X	X	X	X	X	X
SARS-CoV-2 serology test (serum)	X						X			X
Total IgE (serum)	X						X		X	
Allergen-specific IgE (serum)	X									
EDN (plasma)	X			X			X		X	
sST2 (serum)	X						X			
RNA PAXgene	X						X			
CCI [REDACTED]	CI									
CCI [REDACTED]	CI									
DNA for exploratory genetics evaluation (optional)	X ⁱ									
Collect urine for:										
Urinalysis	X		X	X	X	X	X			X
Pregnancy test ^j	X			X	X	X	X		X	X

Table 2 Schedule of Activities: Study Intervention and Follow-up Periods

Period	Study Intervention							Follow-up		
Visit Number	SV4 (Randomisation)	SV5 (TC)	SV6	SV7	SV8	SV9	SV10	SV11	SV12	E/D
Study Day	1	2	8 (± 3)	29 (± 3)	57 (± 3)	85 (± 3)	113 (± 3)	141 (± 3)	169 (± 3)	
Study Week	0	0	1	4	8	12	16	20	24	
Collect nasal sample for:										
Nasal mucosal sampling (lining fluid)	X			X	X	X	X	X	X	
Nasal mucosal sampling (mRNA) ^k	X						X			
Verify eligibility criteria	X									
Randomisation	X									
Study intervention administration^l	C			C	C	C				
Pandemic impact assessment^m	X	X	X	X	X	X	X	X	X	X
Exploratory cough sub-study only										
At-home cough monitoring (for the 24 hours post-clinic visit)							X			
Cough VAS							X			

^a Airway oscillometry and spirometry performed 4 hours (± 15 minutes) post administration of study intervention will require 4 hours withhold of bronchodilator (see Section 6.5.3).

^b Brief physical examination.

^c Complete physical examination.

^d Triplicate ECG. The mean value of each parameter from the triplicate will be used as the baseline value.

^e Echocardiogram and NT-proBNP assessments also to be performed as required, for participants who might be experiencing heart failure, or as soon as possible after heart failure might have occurred.

^f May be performed at any time at or between SV9 (Week 12) and SV10 (Week 16) inclusive.

^g Testing may be performed at any point for a participant suspected of having COVID-19.

^h Prior to administration of study intervention on days when study intervention is administered.

Table 2 Schedule of Activities: Study Intervention and Follow-up Periods

Period	Study Intervention							Follow-up		E/D
Visit Number	SV4 (Random- isation)	SV5 (TC)	SV6	SV7	SV8	SV9	SV10	SV11	SV12	
Study Day	1	2	8 (± 3)	29 (± 3)	57 (± 3)	85 (± 3)	113 (± 3)	141 (± 3)	169 (± 3)	
Study Week	0	0	1	4	8	12	16	20	24	

ⁱ If not performed at SV4, can be performed at any subsequent visit. As a last resort if the participant has completed the study (and not withdrawn consent) but the sample has not been received by the analysing laboratory, the site should ask the participant if he/she would be willing to attend an additional optional visit to provide this sample.

^j Female participants of childbearing potential only.

^k If deemed by investigator to be intolerable for individual participant at SV4 (eg, due to nasal polyps), subsequent assessments may be omitted. If this assessment is not performed at SV4 for any reason, it should not be repeated at SV10.

^l Participants should be monitored for a minimum of one to 2 hours after administration of study intervention (see Section 8.2.3). If a suspected anaphylactic reaction occurs during or within a 24-hour period after administration of study intervention, blood samples for serum tryptase will be collected as soon as possible after the event, at 60 ± 30 minutes after the event, at discharge, and between 2 and 4 weeks post-discharge. Immediate care of the participant and treatment of the reaction must take priority over collecting blood samples. Additional details on anaphylactic reactions are provided in Appendix G and Appendix H.

^m For COVID-19 mitigation, please see Section 2.3.1.2.

ACQ-6 = asthma control questionnaire-6; AE = adverse event; BD = bronchodilator; COVID-19 = coronavirus disease 2019; CRS = chronic rhinosinusitis; E/D = early study intervention discontinuation; ECG = electrocardiogram; EDN = eosinophil derived neurotoxin; FeNO = fractional exhaled nitric oxide; IgE = immunoglobulin E; IL = interleukin; mRNA = messenger RNA; NT-proBNP = N-terminal prohormone of B-type natriuretic peptide; PGI-BR = patient global impression of benefit/risk; PK = pharmacokinetic(s); SAE = serious adverse event; SARS-CoV-2 = severe acute respiratory syndrome coronavirus 2; SGRQ = St George’s respiratory questionnaire; SNOT-22 = sino-nasal outcome test-22; CCI SOC = standard of care; sST2 = soluble ST2; SV = study visit; TC = telephone contact; VAS = visual analogue scale.

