
To assess the safety and tolerability of MEDI3506 compared with placebo, in adult participants with uncontrolled moderate-to-severe asthma.
	
During the intervention and follow-up periods:
 
 • AEs, SAEs, AESIs • Vital signs • Clinical chemistry, haematology, and urinalysis • ECGs • LVEF as measured by echocardiogram • NT-proBNP • Number of participants seropositive for SARS-CoV-2 at end of study who were seronegative at randomisation visit • For participants testing positive for SARS-CoV-2 (by PCR or serology test), during the intervention and follow-up periods, the number and proportion of patients with COVID-19 AEs/SAEs and the proportion asymptomatic.
Exploratory	

To further assess the longitudinal effect of MEDI3506 compared with placebo on lung function in adult participants with uncontrolled moderate-to-severe asthma.
	
As measured at home, change from baseline up to Week 24 in 2-weekly mean PEF and FEV₁

To assess the effect of MEDI3506 compared with placebo on airway hyperresponsiveness in adult participants with uncontrolled moderate-to-severe asthma.
	
Change from baseline to Weeks 8 and 16 in FEV₁% reversibility.

To assess the effect of MEDI3506 compared with placebo on asthma related inflammatory blood biomarkers in adult participants with uncontrolled moderate-to-severe asthma.
	
Change from baseline to Weeks 1, 4, 8, 12, 16, 20 and 24 in inflammatory blood biomarker levels, including but not limited to:
 
 • CCI • Serum IL-5. • Serum IL-13. • Serum TSLP. 
Change from baseline to Weeks 4, 16, and 24 in plasma EDN.
 
Change from baseline to Weeks 16 and 24 in total IgE.
 
Change from baseline to Week 16 in:
 
 • sST2. • Proinflammatory gene signatures in whole blood.

Table 4 Objectives and Endpoints

Objective	Endpoint
To assess the longitudinal effect of MEDI3506 compared with placebo on small airway function in adult participants with uncontrolled moderate-to-severe asthma.	Change from baseline to Weeks 1, 4, 8, 12, and 16 in airway reactance and resistance as assessed by AO parameters, including but not limited to: 
 • R5 • R20 • R5-R20 • AX

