- During the intervention period, participants will be required to take their asthma controller therapy regularly, complete the eDiary and perform lung function tests using a spirometry device at home regularly.
- An automated alert to the participant and site will be triggered if there is a clinically significant deterioration in any of the eDiary data points (as defined in Section 8.1.5) for > 2 days, prompting the participant to contact the investigator for further assessment of a possible asthma exacerbation. Alerts will only be received by site when eDiary uploads/syncs on adequate mobile or broadband signal; therefore, participants may initiate contact with the investigator for assessment of possible exacerbation regardless of any prompts from the site, or the eDiary and spirometry.

Follow-up Period

- Participants who complete the 16-week intervention period visit will complete an 8-week post-treatment follow-up period.
- Participants will be required to take their SOC asthma controller medications throughout the follow-up period.

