8.1.2 At-home Spirometry

During the study period, participants will be required to monitor lung function at home twice daily using an at-home spirometry device. Participants should follow the relevant medication and other restrictions beforehand (Section 5.3.2 and Section 6.5.3). Further details will be provided in a separate instruction manual.

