If the end date of the first CompEx event and the start date of the second CompEx event are less than 7 days apart for any subject, then these will be counted as one CompEx event.

For CompEx analyses, only on-treatment events (based on the period from baseline to last dose date +28 days) will be considered. A supplementary analysis including events in the period from baseline to end of follow-up (Week 24) will also be conducted.

Time-to-first event will be defined as: [Start date of first event or censoring – date of 1st dose] + 1.

Date of first event will be the first start date of a CompEx event as defined above. For participants who do not experience an on-treatment CompEx event, date of censoring will be the minimum between the date of last dose plus 28 days, and the last day of eDiary recording during the on-treatment period. For the analysis of CompEx during combined treatment and follow-up period, date of censoring will be the minimum between the date of end of study visit, and the last day of eDiary recording during combined treatment and follow-up period .

For recurrent events, there must be a gap of 7 days between events ie, at least 7 days between end date of first CompEx event and start date of second CompEx event. Events that occur closer in time will be collapsed into one event.

The time during the event and the 7 days after each event will not be considered when defining time at risk for the CompEx event rate. Time at risk will be defined as [Date of last treatment plus 28 days– date of 1st dose] + 1 – recovery time. For the analysis of CompEx during combined treatment and follow-up period, the time at risk will be defined as [date of end of study visit – date of 1st dose] + 1 – recovery time.

The annualised rate of asthma CompEx events, during intervention period (Baseline to last dose date +28 days) per participant will be calculated as:

Annualised rate of asthma CompEx events during intervention period =

Total number of asthma CompEx events

$$\frac{\text{Total number of asthma CompEx events}}{(\text{Date of last dose of IP} + 28 - \text{Date of the first dose of IP} - \text{recovery time} + 1)/365.25}$$

where the recovery time is defined as:

$$\sum_{i=1}^k [\min(i^{\text{th}} \text{ event end date} + 7, \text{date of last dose} + 28) - i^{\text{th}} \text{ event start date} + 1]$$

The annualised rate of asthma CompEx events, during intervention and follow-up periods (Baseline to Week 24) per participant will be calculated as:

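### The protocol contradicts itself on whether the eDiary and home spirometry continue after Week 16, while exploratory diary endpoints and a supplementary CompEx analysis run to Week 24

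*Protocol*

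**What the plan says.** **Text that points to stopping at Week 16**

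- Protocol Section 1.3 sets home collection period by period. Table 1 has "Twice daily throughout screening period"; Table 2, which covers both the intervention and follow-up periods, has "Twice daily throughout the intervention period".
- Protocol Section 4.1, under the intervention period, requires participants to "complete the eDiary and perform lung function tests using a spirometry device at home regularly". The follow-up list that comes next names neither the diary nor home spirometry; its only requirement on participants at home is "Participants will be required to take their SOC asthma controller medications throughout the follow-up period".

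**Text that points to Week 24**

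- Protocol Section 8.1.2: "During the study period, participants will be required to monitor lung function at home twice daily". Section 8.1.8.1 uses the same study-wide scope for the eDiary.
- In Table 2, the row directly below the diary row schedules a check of eDiary and home spirometry adherence at visits that include SV11 (Week 20) and SV12 (Week 24).
- Protocol Section 3, Table 4, has the exploratory endpoint "change from baseline up to Week 24 in 2-weekly mean PEF" and FEV1 measured at home. Rescue use also runs up to Week 24, and symptom score and night-time awakenings include Weeks 20 and 24.
- SAP Section 3.1.4 defines two-weekly periods to the morning of Day 169, and SAP Section 3.6.2 uses device data through Week 24.
- SAP Section 3.4.6: "A supplementary analysis including events in the period from baseline to end of follow-up (Week 24) will also be conducted". SAP Section 6 lists this as an addition to the protocol.

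SAP Section 3.4.6 also treats the two Week 24 CompEx analyses differently. Time to first event is censored at the earlier of the end-of-study visit and the last eDiary day. Time at risk for the event rate runs to the end-of-study visit, less recovery time, with no reference to the last eDiary day.

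**The concern.** Sites work from the Schedule of Activities. A coordinator who reads the diary row of Table 2 alongside Section 4.1 could reasonably tell participants that home entries end at SV10. Five diary measures (home PEF, home FEV1, rescue use, symptom score, awakenings) would then have no data for Weeks 18 to 24 at that site. A CompEx event is either an asthma exacerbation or a diary event. Without a diary, only the first kind can be seen in follow-up, but the rate's denominator would keep growing. If sites read the text differently, missing diary data in follow-up would also vary by site.

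**Working it through.** The point concerns a collection window, so the check is calendar arithmetic.

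**1. Reproduce the stated periods.** Table 2 puts SV10 on Day 113 and SV12 on Day 169. (169 − 113)/7 = 8 weeks of follow-up, and 5 + 16 + 8 = 29 weeks in total. Both match Protocol Section 4.1.

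**2. Count the two-weekly periods in follow-up.** In SAP Section 3.1.4, period k runs from the evening of Day 1 + 14(k − 1) to the morning of Day 1 + 14k. A start on or after Day 113 needs k ≥ 9. Periods 9 to 12 (Weeks 18, 20, 22, 24) therefore lie in follow-up: 4 of 12.

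**3. Apply the 10-day rule.** SAP Section 3.1.4 sets a two-weekly value to missing with fewer than 10 complete days, each being an evening entry plus the next morning's. If the diary stops at SV10 on Day d, Period 9 has d − 113 complete days.

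- d = 113 gives 0; d = 116 (the end of the ±3-day window) gives 3. Both are below 10.
- Protocol Section 2.3.1.2 allows pandemic-related rescheduling within 14 days, so d could reach 127. Period 9 would then survive if d ≥ 123.
- Periods 10 to 12 have no complete days in any of these cases.

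**4. Week 24 CompEx time at risk, ignoring recovery time.** With the end-of-study visit on Day 169, time at risk is 169 − 1 + 1 = 169 days. With the diary stopped at Day 113, the days without diary-event ascertainment are 169 − 113 = 56, and 56/169 = 33%. The denominator is 169/113 = 1.50 times the diary-observable time.

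**5. Effect on the absolute rate.** Take constant daily rates, e for exacerbations and r for events seen only through the diary. If every participant stopped at Day 113:

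observed rate = (169e + 113r)/169 = e + 0.669r

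The diary component is 33% too low. Let s = r/(e + r) be the diary share of events, and p the fraction of participants at sites that stop at SV10. The total rate is then too low by 0.331 × p × s. The documents give neither p nor s, so these are assumed values:

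| p × s | Shortfall in total rate |
|---|---|
| 0 | 0% |
| 0.25 | 8% |
| 0.50 | 17% |
| 1 | 33% |

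**6. Effect on the rate ratio.** Each arm's observed rate is its true rate times (1 − 0.331 p s). If p and s are the same in both arms, the factor cancels. The documents give no arm-specific values, so no bias in the ratio can be derived.

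**7. Main CompEx analyses.** These count events to the last dose plus 28 days (SAP Section 3.4.6). SAP Section 3.5.2 places the last dosing visit at SV9, Day 85, and 85 + 28 = Day 113. They do not rely on follow-up diary data.

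**The case against.** The best reply is that the documents taken together assume collection through Week 24, and that Table 2 and Section 4.1 simply carry a phrase that was never aligned. The adherence checks at SV11 and SV12 make little sense otherwise. The SAP's censoring rule for the combined period refers to eDiary recording in follow-up. Section 4.1 describes the intervention period and does not say that entries then stop; silence in the follow-up list is not a prohibition. Protocol Section 8.1.8 says that entry windows are programmed into the device, which prompts the participant, so collection may not depend on how a site reads one cell.

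Most of this stands. A reader might infer that the Schedule of Activities is binding, that sites will therefore collect nothing after Week 16, and that the late diary endpoints cannot be derived. The documents do not support that. Protocol Section 8 says that the schedule summarises procedures and timing, and it requires adherence to the design including the schedule, but it does not rank the schedule above Sections 8.1.2 and 8.1.8.1. The schedule also contains the adherence row that points the other way.

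A reader might also infer that the Week 24 CompEx treatment comparison is biased. Time to first event is already censored at the last eDiary day, and step 6 shows that a common cutoff cancels in the rate ratio when the event mix is similar across arms.

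The objection does not remove the conflict between adjacent rows of Table 2, or between Section 4.1 and Section 8. The documents also do not state the last day for which the device is programmed, so different site practice remains possible though not shown.

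**Conclusion.** The contradiction is real and should be reconciled, but its reach is limited. At a site that applied the Table 2 row literally, Periods 9 to 12 would be missing for its participants; Period 9 could survive only with a pandemic-rescheduled SV10. The 33% is an upper bound for the diary component of one supplementary rate. It assumes that the diary stops at Day 113 for everyone, that rates are constant, and that recovery time is ignored. The loss in the total rate is smaller in proportion to p × s.

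The affected diary endpoints are exploratory and the Week 24 CompEx analysis is supplementary. The primary endpoint, in-clinic pre-bronchodilator FEV1 at Week 16, and the main CompEx analyses are unaffected. The different end dates in the SAP for the Week 24 CompEx rate and time to first event merit correction whichever window is intended.

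**What to change.** **Protocol.** Change the Table 2 diary row and the Section 4.1 text to twice daily through SV12 (Week 24), so that they agree with Sections 8.1.2 and 8.1.8.1. This costs one table cell and one sentence. Participants already hold the device and the adherence checks at SV11 and SV12 are already scheduled. The small downside is eight more weeks of entries for participants at sites that would have stopped at SV10.

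**SAP Section 3.4.6.** For the Week 24 CompEx rate, end both time at risk and event counting at the earlier of the end-of-study visit and the last eDiary day, as the time-to-first-event analysis already does. Do this at least as a sensitivity analysis. The cost is that it drops later time in which exacerbations are still recorded, which is a reason to show both versions.

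**If diary collection is meant to stop at SV10.** Limit the diary outputs and the CompEx analyses to Week 16, and bring Sections 8.1.2 and 8.1.8.1, Table 4 and the adherence row into line.
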